Orginal Title: Evaluation of Anthropometric and Ultrasonographic Measurements With Different Machine Learning Methods in Predicting Difficult Intubation: A Prospective Observational Study

Brief Title: Anthropometric and US-Guided Difficult Intubation Prediction With ML Models

NCT Number: NCT06904586

UPDATE DATE: 20.04.2025

ETHICS APPROVAL DATE: 18.04.2022

Statistical Analysis Plan

It is reported in the literature that the rate of difficult intubation is approximately 17% (3). This study determined the minimum sample size required to detect a statistically significant difference (effect size= 0.1) as 273 individuals under 95% power and 5% type I error conditions. Power analysis was performed with the PASS v.15 demo program.

Machine Learning Algorithms

The data labeled with expert opinion on whether there was a difficult intubation was classified using 8 different machine learning algorithms, which are among the most widely used classification algorithms in the literature and have proven success in this field. These algorithms are; Logistic Regression (LR) , Support Vector Machine (SVM) , Random Forest (RF), K-Nearest Neighbors (KNN), Gaussian Naive Bayes (GNB) , CatBoost, XGBoost ve Decision Tree (DT). These algorithms were applied to the dataset, and the results were obtained.

The 15 most affecting features determined by the feature extraction method from the 30 parameters in the dataset were selected and the dataset was prepared for the classification process according to these features. In addition, different pre-processing methods, such as editing and categorizing the "null" values, were applied to the dataset.

Models were created for each algorithm. The data set was evaluated in 2 groups: 80% training and 20% testing. After training and testing each model with data, the results were obtained. K-fold Cross-validation, the training data is divided into k equal parts. The divided parts are used for both training and testing. 5-Fold cross-validation was performed on the training data. This prevented overfitting of the data.

PROTOCOL

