2. Distance from the skin to the epiglottis (DSE) at the midpoint between the hyoid bone and the thyroid cartilage at the level of the thyrohyoid membrane
3. Minimum distance from the skin to the vocal cord anterior commissure (DSAC) at the level of the anterior commissure
4. Distance between the skin and the trachea (DST) 2 cm above the sternal notch, with the trachea seen transversely
5. Maximum tongue thickness in the sagittal axis under the chin with a 1- 8 MHz convex probe while the patient was in the neutral position.
6. The distance from the hyoid bone shadow to the mentum via the convex probe while the patient's neck is in extension (DSHBE) and neutral (DSHBN) positions. All USG evaluations were performed by an independent trained anesthesiologist.

Patients were induced with 2-2.5 mg/kg propofol, 1 mcg/kg fentanyl and 0.6 mg/kg rocuronium.

Mask-ventilated patients were intubated by direct laryngoscopy by an anesthesiologist with different professional experience after the count became 0 with neuromuscular monitoring using GE Healthcare's line of NMTR accessories. Cormack-Lehane score was recorded. Patients who could not be intubated were taken over by more experienced specialist physicians. Patients who could not be intubated by direct laryngoscopy by an anesthesiologist with 5 years or more experience, who used video laryngoscopy, fiberoptic bronchoscopy, and who required stylet, bougie, and cricoid pressure in addition to video laryngoscopy were evaluated as having difficult intubation.

The data obtained from the patients were subjected to various pre-processing steps to make them suitable for classification. Although there are many methods for pre-processing, the pre processing steps applied to the data set used in this study were the editing of null data, categorization of data, and feature extraction. After the completion of the null data, the textual data in the data set was converted to categorical data. Since there was little difficult intubation data in the data set, data augmentation was performed to prevent memorization in the data.

Data balancing was performed for the difficult intubation class, which was in the minority, using SMOTE (Synthetic Minority Over-Sampling Technique). SMOTE increased the samples of the minority classes and balanced the unbalanced classes.

Machine Learning Algorithms

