The data labeled with expert opinion on whether there was a difficult intubation was classified using 8 different machine learning algorithms, which are among the most widely used classification algorithms in the literature and have proven success in this field. These algorithms are; Logistic Regression (LR), Support Vector Machine (SVM), Random Forest (RF), K-Nearest Neighbors (KNN), Gaussian Naive Bayes (GNB) , CatBoost, XGBoost ve Decision Tree (DT). These algorithms were applied to the dataset, and the results were obtained.

The 15 most affecting features determined by the feature extraction method from the 30 parameters in the dataset were selected and the dataset was prepared for the classification process according to these features. In addition, different pre-processing methods, such as editing and categorizing the "null" values, were applied to the dataset. Models were created for each algorithm. The data set was evaluated in 2 groups: 80% training and 20% testing. After training and testing each model with data, the results were obtained. K-fold Cross-validation, the training data is divided into k equal parts. The divided parts are used for both training and testing. 5-Fold cross-validation was performed on the training data. This prevented overfitting of the data.

FLOW CHART

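### No scaling of continuous features is described before SMOTE, KNN and SVM, so the units of measurement can decide which predictors drive them

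*Combined protocol and SAP*

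**What the plan says.** The pre-processing paragraphs of the protocol, just before its Machine Learning Algorithms heading, state that the pre-processing "steps applied to the data set used in this study were the editing of null data, categorization of data, and feature extraction". Categorization is then explained: "After the completion of the null data, the textual data in the data set was converted to categorical data". It concerns text fields and is not a rescaling of measurements. Two further steps are reported separately. One is augmentation: "Since there was little difficult intubation data in the data set, data augmentation was performed to prevent memorization in the data". The other is balancing of the minority class "using SMOTE (Synthetic Minority Over-Sampling Technique").

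The Statistical Analysis Plan, repeated under the protocol's Machine Learning Algorithms heading, is looser: "In addition, different pre-processing methods, such as editing and categorizing the 'null' values, were applied to the dataset". Its only examples concern null values.

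The algorithms, besides logistic regression, are "Support Vector Machine (SVM), Random Forest (RF), K-Nearest Neighbors (KNN), Gaussian Naive Bayes (GNB) , CatBoost, XGBoost ve Decision Tree (DT"). On their inputs, both parts say: "The 15 most affecting features determined by the feature extraction method from the 30 parameters in the dataset were selected". The 15 are not named. The protocol records age, weight, height, BMI, tape-measured lengths and ultrasound distances without units. The SVM kernel and the KNN distance metric are not given either.

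**The concern.** In their usual forms KNN and SMOTE choose neighbours by Euclidean distance, and SVM also depends on the scale of its inputs. With raw units, a feature counts in proportion to its variance in whatever unit it was typed, so a length entered in mm counts 100 times as much as the same length in cm. Tree-based methods, Gaussian Naive Bayes and unpenalised logistic regression are essentially indifferent to linear rescaling.

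Two things are at stake. Differences between the algorithms could partly reflect data entry units. The ultrasound measurements, which the study sets out to evaluate, could be weighted up or down for reasons unrelated to their predictive value. SMOTE output feeds every model trained on the balanced data, so any distortion of its neighbours is not confined to KNN and SVM.

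**Working it through.** The plan states no figure on this point, so there is none to reproduce. The check has two parts: what sets the distances, and what that costs.

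**1. Share of squared distance.** For two randomly chosen patients the expected squared Euclidean distance is 2 × Σ SD². Feature j therefore contributes SD_j² / Σ SD², whatever the correlations. The documents give no SDs, so all of these are assumptions, for 19 features built from variables named in the protocol:

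- age 16 y, weight 15 kg, height 9.5 cm: 256 + 225 + 90.25 = 571.25
- BMI 5: 25
- Mallampati 0.8, ULBT 0.6, sex 0.5, ASA 0.6: 1.61
- tape lengths in cm (thyromental 1.2, neck 4, mouth opening 0.8, sternomental 2): 22.08
- seven ultrasound distances in cm (0.25, 0.4, 0.25, 0.35, 0.6, 0.7, 0.6): 1.6175

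A change from cm to mm multiplies a block by 100. Height stays in cm throughout.

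| Units | Total | Age + weight + height | Tape | Ultrasound |
|---|---|---|---|---|
| All cm | 621.56 | 571.25/621.56 = 91.9% | 3.6% | 0.3% |
| Tape cm, ultrasound mm | 781.69 | 571.25/781.69 = 73.1% | 2.8% | 20.7% |
| Tape and ultrasound mm | 2967.61 | 571.25/2967.61 = 19.2% | 74.4% | 5.5% |

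Other plausible SDs give 91% for the first row, 67 to 69% for the second and 18% for the third. If feature selection dropped age, weight and height, their share is 0% and others dominate: BMI in the first row (25/50.31 = 49.7%), ultrasound in the second (161.75/210.44 = 76.9%), tape lengths in the third (2208/2396.36 = 92.1%). After standardisation the three carry 3/19 = 16%, or 3/15 = 20% if all are among the 15 selected.

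**2. Cost in discrimination.** The simulations used 263 training patients (80% of 329), 17% events, SMOTE on training data only and KNN with k = 5. SDs were assumed and close to those above. The SVM used a radial kernel. AUC is the reviewer's choice, as the documents name no metric.

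| Where the signal was placed | Units and features | Method | Unscaled | Scaled |
|---|---|---|---|---|
| Mainly ultrasound | all cm | KNN | 0.51 | 0.62 |
| Mainly ultrasound | all cm | SVM | 0.53 | 0.70 |
| Mainly ultrasound | ultrasound mm | KNN | 0.57 | 0.62 |
| Mainly ultrasound | ultrasound mm | SVM | 0.65 | 0.70 |
| Age, weight, BMI, neck | all cm | KNN | 0.611 | 0.612 |
| Age, weight, BMI, neck | ultrasound mm | KNN | 0.617 | 0.618 |
| Ultrasound | ultrasound mm; age, weight, height dropped | KNN | 0.605 | 0.604 |

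With evenly spread signal, KNN lost 0.04 to 0.06. A separate set of KNN runs lost about 0.03 to 0.09 when signal was in ultrasound or evenly spread, with the same exception as the last row. In the settings with signal mainly in ultrasound, logistic regression (0.74 to 0.75) and random forest (0.69 to 0.70) barely moved.

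**The case against.** The strongest reply is that silence is not omission. Augmentation and SMOTE lie outside the three-item list, so that list is not closed, and the SAP's wording is open. The documents never say that scaling was not done, and they omit other technical settings too. This stands in part: undocumented scaling cannot be excluded. But the protocol gave augmentation and SMOTE sentences of their own and gave scaling none, so an analyst following the text would not scale.

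A reader might infer three stronger things, none of which the documents support:

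- **That weight, height and age set the distances almost wholly.** This needs them to be among the 15 unnamed features and the lengths to be in cm. The share runs from 0% to about 92%.
- **That ultrasound has almost no say.** It carries about 21% with ultrasound in mm, and 77% if age, weight and height are also dropped. The latter exceeds its equal share of 7/16 = 44%.
- **That the ranking of algorithms is wrong.** In the simulations with signal mainly in ultrasound, logistic regression was first and KNN last with or without scaling; at most SVM drew level with random forest. The documents name no metric or ranking rule and do not say where the signal lies. With signal in body-size variables the penalty vanished.

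The test set is also small: 20% of 329 is about 66 patients, or about 11 events at 17%. The Hanley-McNeil standard error of an AUC of 0.70 is then about 0.09, so a loss of 0.05 would be hard to see. That limits what the comparison can show; it does not remove a systematic handicap.

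**Conclusion.** The point holds in conditional form. As described, the pipeline has no scaling of continuous features, so KNN, SVM and the SMOTE neighbours follow the features with the largest numeric spread. Which features those are depends on the units and the retained set, neither of which is given. Units can handicap KNN and SVM relative to tree methods, Gaussian Naive Bayes and unpenalised logistic regression. The size runs from nil to moderate for KNN (at most 0.62 − 0.51 = 0.11 in AUC). For SVM, simulated only with signal mainly in ultrasound, it was 0.05 to 0.17. These sizes rest on assumed SDs, default settings and an assumed location of the signal. A changed ranking is not shown. Confidence is medium, because scaling may have been done and not reported. The step is worth adding because it removes an arbitrary influence at almost no cost.

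**What to change.** Add a standardisation step for continuous features. Compute the mean and SD on the training fold only, and apply them unchanged to the held-out fold and the test set. Place the step before SMOTE, KNN, SVM and any penalised logistic regression, then rerun the eight-algorithm comparison. Name the 15 selected features and their units so that readers can judge the effect.

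If scaling was already done, say so and state on which data it was fitted. In that case, provided it was fitted on training data only, just the text changes. Otherwise the cost is one pipeline step and a rerun, with no new data.

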Ethics committee approval numbered 2022/65 was received from the Düzce University Non Interventional Health Research Ethics Committee. Our study, which received project support numbered 2023.04.04.1402 from Düzce University Scientific Research Projects Coordinatorship, was designed as a prospective, observational study in the Anesthesiology and Reanimation Clinic of the Faculty of Medicine Hospital. Informed consent was obtained from all patients.

Patients over the age of 18 who underwent general anesthesia and had an American Society of Anesthesiologists (ASA) score between I-III were included in the study. Patients who had undergone or were planned to undergo head and neck surgery, who were scheduled to undergo thyroidectomy, who had congenital or acquired morphological disorders, and who had a history of difficult airways were excluded from the study.

It is reported in the literature that the rate of difficult intubation is approximately 17%. This study determined the minimum sample size required to detect a statistically significant difference (effect size= 0.1) as 273 individuals under 95% power and 5% type I error conditions. Power analysis was performed with the PASS v.15 demo program.

329 patients who met the inclusion criteria were included in the study. Following routine vital monitoring (ECG, SpO₂, NIBP) in the preoperative evaluation room, age, gender, weight, height, body mass index (BMI), Modified Mallampati score, and upper lip bite test (ULBT) values were recorded.

Anthropometric lengths were measured as described with the help of a tape measure;

1. Thyromental distance: the distance from the thyroid notch to the lower tip of the chin when the patient's head is in a neutral position
2. Neck circumference: the measurement around the entire neck with the help of a tape measure, just below the thyroid cartilage
3. Mouth opening distance: the distance between the upper and lower incisors at maximum mouth opening
4. Sternomental distance: the length from the sternal notch to the mentum when the neck is extended

The ultrasonic evaluation was performed with the 4- 15 MHz linear probe of the Esaote MayLab sevenR ultrasound in the supine position, with the head and neck in a neutral position. The distances

to the anterior neck surface were obtained by placing the linear probe in a transverse position at three different levels;

1. Minimum distance from the hyoid bone to the skin surface (DSHB) at the level of the hyoid bone

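### Augmentation is credited with preventing memorization, but SMOTE adds no independent difficult intubations and does not reduce overfitting; no use of cross-validation to choose model complexity is described

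*Combined protocol and SAP*

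**What the plan says.** The pre-processing text of the Protocol section, just before its Machine Learning Algorithms heading, gives augmentation a protective purpose: "Since there was little difficult intubation data in the data set, data augmentation was performed to prevent memorization in the data". The next paragraph names SMOTE, applied to the difficult-intubation class, and describes its effect: "SMOTE increased the samples of the minority classes and balanced the unbalanced classes". No other augmentation method is named.

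The Statistical Analysis Plan section does not mention augmentation or SMOTE. Both sections, under Machine Learning Algorithms, carry three further statements that bear on overfitting:

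- a hold-out: "The data set was evaluated in 2 groups: 80% training and 20% testing";
- a reduction of inputs: "The 15 most affecting features determined by the feature extraction method from the 30 parameters in the dataset were selected";
- cross-validation: "5-Fold cross-validation was performed on the training data. This prevented overfitting of the data".

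Neither section states a tuning rule, tree depth, leaf size, number of neighbours or penalty, or says what the cross-validation was used to decide.

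**The concern.** A model memorizes when it fits the particular patients it was trained on and so performs better on them than on new ones. The usual protections are more independent patients or a less flexible model. SMOTE supplies neither. It places new points on the lines between existing difficult cases, so the row count rises while the number of independent difficult intubations stays the same. For a nearest-neighbour method it can make matters worse, because each real difficult case becomes surrounded by points derived from it.

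If readers accept the stated rationale, they will believe that the small event class has been dealt with. They may then see no need for the step that would help, which is choosing each algorithm's complexity. In a comparison of eight algorithms of very different flexibility, that choice affects both how each performs in new patients and how they rank.

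**Working it through.** **Figures in the plan.** The documents give no count of difficult intubations and no measure of overfitting, so there is no figure on this point to reproduce. The planned sample size of 273 plays no part.

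**Inputs.**
- Patients, Protocol section: "329 patients who met the inclusion criteria were included in the study".
- Event rate, both sections: "It is reported in the literature that the rate of difficult intubation is approximately 17" per cent. This is a literature figure, so 5% and 10% are shown as assumed alternatives.
- Training share 80%; 15 features after selection.
- Balancing is read as 1:1 (assumption).

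**Step 1: real and synthetic cases in training.** Training patients = 329 × 0.80 = 263.2. With event rate r, real cases = 263.2 × r, other patients = 263.2 × (1 − r), and synthetic rows = the difference.

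| Rate | Real difficult | Others | Synthetic rows | Synthetic per real | Synthetic share of difficult class |
|---|---|---|---|---|---|
| 17% | 44.7 | 218.5 | 174 | 3.9 | 79% |
| 10% | 26.3 | 236.9 | 211 | 8.0 | 89% |
| 5% | 13.2 | 250.0 | 237 | 18.0 | 95% |

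The real-case column is the information available, and SMOTE does not change it.

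**Step 2: does SMOTE narrow the gap?** Gap = AUC on real training patients minus AUC in new patients. Assumed settings: 263 training patients, 17% events, 15 features, SMOTE with 5 neighbours on training rows only, 80 replicates, 4,000 new patients.

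Pure noise (true AUC 0.50):

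| Algorithm | Gap without SMOTE | Gap with SMOTE |
|---|---|---|
| SVM, RF, two boosting models, DT | 0.49–0.50 | 0.49–0.50 |
| KNN | 0.31 | 0.46 |
| LR | 0.18 | 0.17 |
| GNB | 0.24 | 0.18 |

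GNB is the only algorithm whose gap fell noticeably, and it gained nothing in new patients.

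With six informative features (log-odds 0.5 per SD), AUC in new patients:

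| Algorithm | Without SMOTE | With SMOTE | Change |
|---|---|---|---|
| LR | 0.750 | 0.744 | −0.006 |
| SVM | 0.692 | 0.685 | −0.007 |
| RF | 0.676 | 0.684 | +0.008 |
| KNN | 0.607 | 0.620 | +0.013 |
| GNB | 0.715 | 0.670 | −0.045 |
| Boosting, first | 0.675 | 0.672 | −0.003 |
| Boosting, second | 0.684 | 0.680 | −0.004 |
| DT | 0.548 | 0.561 | +0.013 |

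A separately coded run (LR, KNN, DT, RF; 60 replicates) agrees. On noise, the KNN gap went from 0.808 − 0.497 = 0.311 to 0.961 − 0.500 = 0.461. LR went from 0.675 − 0.501 = 0.174 to 0.669 − 0.502 = 0.167. DT and RF had training AUC 1.00 with and without SMOTE. With three features shifted by 0.5 SD, the KNN gap went from 0.854 − 0.575 = 0.279 to 0.967 − 0.580 = 0.387.

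**Step 3: does choosing complexity narrow it?** Six informative features, no SMOTE:

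| Change | Gap | New-patient AUC |
|---|---|---|
| DT, minimum leaf 1 to 20 | 0.45 to 0.24 | 0.55 to 0.62 (0.56 to 0.61 in a second run) |
| KNN, k from 5 to 25 | 0.26 to 0.10 | 0.60 to 0.67 |
| KNN, k = 5 v k chosen by 5-fold cross-validation on real patients | 0.25 to 0.05 | 0.60 to 0.70 |

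In the setting of the last row, SMOTE instead widened the KNN gap from 0.25 to 0.35 and left the LR gap at 0.08. It raised mean predicted risk from about 0.17 to 0.38–0.47. LR gained nothing from tuning.

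**The case against.** Several points on the other side stand.

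- A reader might infer that augmentation is the plan's only safeguard. It is not: both sections credit 5-fold cross-validation with preventing overfitting, and both hold out 20%. But these steps measure overfitting. They reduce it in the fitted model only if their results are used to choose complexity, and no such use is described.
- A reader might infer that the trees were fully grown and the flexible learners left uncontrolled. The documents do not support that. The settings are unstated, the folds may have been used for tuning, and the cut from 30 to 15 features is a described limit. For the same reason, the unchanged gap for tree-based models belongs to the assumed unrestricted versions, whose training AUC is near 1.00 with or without SMOTE.
- A reader might infer that SMOTE itself damages performance in new patients. For seven of the eight algorithms, AUC moved by only about 0.01 either way.
- SMOTE has another stated purpose, class balance, and it does change classification at a fixed cut-off. With signal and a 0.5 cut-off, new-patient sensitivity rose from 0.22 to 0.62 for LR, 0.17 to 0.46 for GNB and 0.10 to 0.63 for KNN. LR specificity fell from 0.95 to 0.72. A lower cut-off could do similar work, but the purpose is legitimate, and the documents name no performance measure; AUC is the choice made here.
- Memorization may loosely mean learning only the majority class. If so, the sentence should say that; as written, it claims protection against overfitting.

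Whether SMOTE came before or after the split is also unstated. That is a separate question, and this point holds even if SMOTE was confined to training rows.

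**Conclusion.** The concern holds for the property claimed. SMOTE creates no independent difficult intubations, whatever the event rate. In simulation it did not close the gap between training and new patients: unchanged for tree-based models and SVM, almost unchanged for LR and wider for KNN. GNB's gap narrowed on noise without benefit in new patients.

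The finding is a wrong rationale together with an undescribed step, the choice of complexity. It does not show that the fitted models were uncontrolled or that SMOTE made them worse. The benefit of choosing complexity was shown for KNN (about 0.10 in new-patient AUC) and decision trees (0.05 to 0.07), not for LR. These sizes rest on the assumed 17% rate, 1:1 balance, simulated features and default-type settings. The count argument needs none of the simulation assumptions.

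**What to change.** 1. In the Protocol section, delete the clause that gives preventing memorization as the purpose of augmentation. The Statistical Analysis Plan section has no matching sentence to remove.
2. State in both sections that the existing 5-fold cross-validation, scored on real patients only, chooses the complexity of each tunable algorithm: k for KNN; leaf size or depth for DT, RF, XGBoost and CatBoost; penalty for LR and SVM. Give the grid.
3. Report the number of real difficult intubations, overall and in training, and the apparent-minus-out-of-fold AUC gap for each algorithm.
4. Preferably make the fit on real patients primary, with the classification cut-off chosen in the training folds. If SMOTE is kept for class balance, confine it to the training part of each fold and do not present it as protection against overfitting.
5. If the augmentation was a step separate from SMOTE, describe it.

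Cost: a wording change, a small tuning grid in folds the plan already has, and a rerun on data already collected. The downsides are a little more computing and less favourable training-set figures.

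### No readable sentence confines SMOTE to training data: if it came before the 80/20 split, hold-out and 5-fold results are optimistic; if run once on the 80%, the 5-fold results are

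*Combined protocol and SAP*

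**What the plan says.** The paragraphs of the PROTOCOL part just before *Machine Learning Algorithms* deal with data preparation. They open: "The data obtained from the patients were subjected to various pre-processing steps to make them suitable for classification". The steps are then listed as "the editing of null data, categorization of data, and feature extraction", a list without SMOTE. Two statements about the rare class follow: "Since there was little difficult intubation data in the data set, data augmentation was performed to prevent memorization in the data", and then "Data balancing was performed for the difficult intubation class, which was in the minority, using SMOTE (Synthetic Minority Over-Sampling Technique". The stated outcome is that "SMOTE increased the samples of the minority classes and balanced the unbalanced classes".

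The next section, *Machine Learning Algorithms*, says in its first paragraph that "These algorithms were applied to the dataset, and the results were obtained". Only afterwards does it describe the partition, "The data set was evaluated in 2 groups: 80% training and 20% testing", adding: "After training and testing each model with data, the results were obtained". Five-fold cross-validation is placed on the training data, and the section closes by claiming that overfitting was thereby prevented.

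The Statistical Analysis Plan part repeats the split and the cross-validation but mentions neither augmentation nor SMOTE. The PROTOCOL part ends with a flow chart whose content is not in the readable text.

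**The concern.** SMOTE builds an artificial difficult case by interpolating between a real difficult patient and one of that patient's nearest difficult neighbours. If the artificial row and its parents fall on opposite sides of a training/test boundary, the model is scored on cases it has partly seen.

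The text ties cross-validation to the training data but ties SMOTE to nothing. Two placements that it leaves open do harm:

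1. **SMOTE before the 80/20 split**, which is the order in which the text runs. Artificial cases share parents across training and test data. Hold-out and 5-fold results are both optimistic, and the hold-out no longer has the clinical event rate.
2. **SMOTE once on the 80%.** The hold-out is clean, but the five folds mix real patients with rows built from them, so the 5-fold results are optimistic. This matters if those results are reported or used to choose among models; the text does not say.

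Only SMOTE redone inside each training fold, with test and validation rows left alone, avoids both.

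What is at stake is the study's main product: how well eight algorithms predict difficult intubation in a new patient, and which does best. The closing claim about overfitting reassures the reader on exactly this risk.

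**Working it through.** The documents give no performance figure and no count of difficult intubations, so there is no figure of the plan's own to reproduce. What follows shows the mechanism and its possible size, for logistic regression (LR), K-nearest neighbours (KNN) and random forest (RF).

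**Inputs.** From the documents: 329 patients; 15 predictors kept; 80/20 split; 5 folds; classes balanced; a literature rate of about 17%. Assumed: 17% also holds in this sample, balancing is to 1:1, and SMOTE uses 5 neighbours.

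**How much of the data would be synthetic.** 0.17 × 329 ≈ 56 difficult and 329 − 56 = 273 not difficult (it equals the stated minimum sample size only by coincidence). Balance needs 273 − 56 = 217 synthetic rows, which is 217/273 = 79% of the difficult class. At 10% events the share is 263/296 = 89%; at 25% it is 165/247 = 67%.

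**How often a synthetic test row is linked to training data.** Each row has two real parents, each in the training part with probability about 0.8. At least one is there with probability about 1 − 0.2 × 0.2 = 0.96.

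**Placement 1, simulated hold-out AUC.** 15 independent normal predictors, no feature selection, 60 replicates, Monte Carlo SE at most 0.010. Weak and strong signal mean four predictors shifted by 0.5 and 1.0 SD. Clean means trained on the oversampled 80% and scored on fresh patients at the natural rate.

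| Signal | LR: before split v clean | KNN: before split v clean | RF: before split v clean |
|---|---|---|---|
| None | 0.64 v 0.50 | 0.87 v 0.50 | 0.95 v 0.50 |
| Weak | 0.79 v 0.71 | 0.90 v 0.61 | 0.96 v 0.66 |
| Strong | 0.94 v 0.90 | 0.95 v 0.81 | 0.98 v 0.87 |

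These values do not bound the effect. With a 1.5 SD shift the excess falls to about 0.015 for LR and 0.04 to 0.05 for KNN. With 5% events and a 1 SD shift it is about 0.09 to 0.10 for LR, against 0.04 at 17%.

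**Placement 2, simulated 5-fold AUC**, SMOTE once on the 80% v inside folds (30 replicates, SE at most 0.013):

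| Signal | LR | KNN | RF |
|---|---|---|---|
| None | 0.65 v 0.50 | 0.87 v 0.51 | 0.96 v 0.50 |
| Weak | 0.79 v 0.69 | 0.90 v 0.61 | 0.97 v 0.64 |
| Strong | 0.94 v 0.89 | 0.95 v 0.80 | 0.98 v 0.86 |

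Under this placement the untouched 20% stays at chance when there is no signal: LR 0.502, KNN 0.503, RF 0.514 (a separately coded run, SE at most 0.014).

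**Prevalence under placement 1.** PPV = se·p / [se·p + (1 − sp)(1 − p)]. With sensitivity and specificity 0.80, PPV is 0.80 at p = 0.50, but 0.136/(0.136 + 0.166) = 0.45 at p = 0.17. This matters only if precision is reported; the documents name no metric.

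**Precision of a clean hold-out.** 20% of 329 is about 66 patients, 11 difficult and 55 not. The Hanley-McNeil SE is 0.094 at AUC 0.70, so the 95% half-width is 1.96 × 0.094 = 0.18. At AUC 0.90 it is 1.96 × 0.064 = 0.13.

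**The case against.** The strongest reply is that no leak is shown. Paragraph order is weak evidence of the order of work: the protocol reports that the algorithms had been applied before it describes feature selection or the split. SMOTE is absent from the list of steps applied to the data set, which fits training-only use. The flow chart cannot be seen and might show the order. All of this stands. A reader might infer that the hold-out was contaminated; the documents do not support that, and the point is conditional.

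The AUC figures rest on assumed data, and the linear scenarios favour LR by construction. With a strong signal LR leads when clean (0.899, RF 0.872) and falls behind under the leak (0.935, RF 0.983). A reader might infer that the study's ranking is wrong, but where a flexible method is truly best the leader need not change. CatBoost was not simulated.

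The overfitting claim could be partly defended if the folds were used to choose settings, since that can limit overfitting. The documents do not say what the folds were for, so calling the claim false in every case would go too far. It is still too strong: 5-fold cross-validation does not by itself prevent overfitting.

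Finally, augmentation and SMOTE may be one operation described twice. That changes the wording of the fix, not the point.

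**Conclusion.** The point holds in conditional form. The readable text describes SMOTE before the split and the folds and never confines it to training data. Followed in that order, it makes both sets of results optimistic; run once on the 80%, it makes the 5-fold results optimistic. Which was done is unknown, and so is the study's actual bias.

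The possible size is large enough to matter. Under the stated assumptions, uninformative predictors can reach a hold-out AUC of 0.87 with KNN. The excess is smaller for LR, shrinks as the true signal becomes very strong and grows as events become fewer. Because it differs by algorithm, the ranking of the eight may change but need not. Until the placement is stated, a reader cannot tell whether the hold-out is valid.

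**What to change.** State where SMOTE was applied and whether the augmentation is SMOTE or a further step. Specify in both the protocol and the SAP:

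> The real patients are split 80/20 first, stratified by outcome. SMOTE (and any separate augmentation) is applied only to the training part of the split and, separately, only to the training part of each cross-validation fold. All validation and test results are computed on real patients at natural prevalence.

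Delete the claim that cross-validation prevented overfitting and say what the five folds were actually used for. Report confidence intervals for all performance measures.

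This text alone does not secure a clean hold-out. The choice of 15 from 30 features and the completion of null values must also be confined to training data.

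Cost: if the work was already done this way, one clarifying paragraph. If not, a re-run of the eight algorithms on existing data, with no new patients. The price is less favourable figures and a test set with only about 11 real difficult cases at 17% (7 at 10%, 16 at 25%), which is imprecise for ranking eight algorithms.
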